3.2 END OF STUDY DEFINITION

2024-11-26 (Final data collection date for primary outcome measure)

4 STUDY POPULATION

4.1 INCLUSION CRITERIA

Eligibility criteria include adults who are >18 years old, insufficiently active (engaging in moderate-vigorous physical activity< 60 minutes per week), residents of participating rural Black Belt (Marengo, Choctaw, Sumter, Hale, Greene, Dallas) counties, BMI 18.5-45, no serious medical condition that would make physical activity unsafe (history of heart disease, myocardial infarction, angina, stroke, or orthopedic conditions which limit mobility), not planning to move from the area within the next 18 months, able to speak and read English, willing to be randomized to either study arm and adhere to study protocol, and able to regularly access a telephone (own a cell phone or work/home landline) to complete IVR calls.

4.2 EXCLUSION CRITERIA

Items from the Physical Activity Readiness Questionnaire (PAR-Q) on cardiovascular/musculoskeletal risk factors will be included in this screening, as recommended by the American College of Sports Medicine for moderate intensity physical activity.81,82 Endorsing an item on the PAR-Q will be grounds for ineligibility.

4.3 SCREEN FAILURES

Ineligible respondents will be thanked for their time and given exclusion reasons. Reasons for ineligibility/disinterest will be tracked for CONSORT diagrams.

4.4 STRATEGIES FOR RECRUITMENT AND RETENTION

Recruitment will take place in rural Black Belt AL counties and be led by [name], Community Health Educator, and her team at the Office of Community Outreach and Engagement in the UAB Comprehensive Cancer Center, including county coordinators. Study staff will distribute study flyers, and host study information sessions via Zoom or in local community meeting spaces as feasible (e.g., county health departments, church fellowship halls, etc) in which individuals will receive a study description and be screened for eligibility. We will also consider strategically placed local newspaper and radio advertisements to promote awareness of the study. All recruitment materials will state that transportation and childcare expenses for assessment visits will be covered, as these strategies increased minority participation in our past studies .Moreover, assessments will be completed by local county coordinators (trusted individuals in the community) in convenient community locations.

Retention efforts will include appointment reminders, flexible scheduling,honoraria/nonmonetary incentives, and holiday cards. In the case of 2 or more missed IVR intervention calls, staff will contact the participant to determine the reason why and retrieve missing data. If unable to reach by telephone, a letter will be sent. Moreover, to maintain engagement in the wait list control condition, these participants will be involved in monthly virtual events on cancer topics other than physical activity (e.g., screening) during the wait period.

5 STUDY INTERVENTION

5.1 STUDY INTERVENTION(S) ADMINISTRATION

5.1.1 STUDY INTERVENTION DESCRIPTION

The 12-month multi-level DIAL intervention is based in social ecological model and emphasizes individual, interpersonal, community/ organizational, and policy approaches to increasing PA. Individual and interpersonal strategies are grounded in Social Cognitive Theory (SCT). Participants will report PA and key SCT constructs (self-efficacy, social support, outcome expectations, enjoyment) and receive tailored counseling via IVR. Interpersonal and community/organizational strategies will include support from local coordinators (problem solving barriers, leading walking groups) and monthly newsletters.

5.1.2 DOSING AND ADMINISTRATION

Participants will complete IVR calls each day for 3 months, twice/week in months 4-6, and once/week in months 7-12.

5.2 MEASURES TO MINIMIZE BIAS: RANDOMIZATION

[name] (biostatistician) will prepare a closed envelope blocked randomization for the two treatment arms stratified by county and BMI group (BMI<30 and BMI>30, as this variable is known to be related to activity levels) using Proc Plan in SAS® Ver. 9.4.

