3 STUDY DESIGN

3.1 OVERALL DESIGN

The current study will test the efficacy of a 12-month multi-level, Interactive Voice Response system-supported physical activity intervention vs. a waitlist control condition. Primary endpoints are changes in moderate intensity or greater aerobic physical activity from baseline to 6 months and 12 months. Secondary endpoints include examining effects on physical performance and related psychosocial variables; intervention costs, changes in physical activity from 12-18 months, potential mediators/moderators of intervention efficacy, and barriers and facilitators to the implementation and sustainability of the DIAL intervention. This two armed randomized controlled trial will enroll a sample of 240 underactive adults from rural Black Belt (Marengo, Choctaw, Sumter, Hale, Greene, Dallas) counties in Alabama. Interested individuals will attend study information sessions hosted by local county coordinators to learn more about the study and complete brief screening interviews.

If still eligible and interested, participants will complete the informed consent process and be scheduled for an assessment visit. At this visit, participants will complete measurements (height, weight, waist circumference, 2 Minute Step Test, psychosocial surveys in REDCap) at a community location with their local county coordinator. Accelerometers will be distributed with instructions and a live demonstration of proper wear. Trained UAB staff will coordinate accelerometer data collection (device initialization, delivery, maintenance, etc). Participants will wear the accelerometer for 7 days. Once valid wear protocol is confirmed, participants will complete 7-Day Physical Activity Recall interviews by phone with trained, blinded UAB research

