staff. After all assessment measures are complete, participants will be randomly assigned to a group. Intervention participants will receive orientation to the IVR system and begin the physical activity intervention and the Waitlist Control participants will be encouraged to maintain their normal routine until 6 month assessments. At 6-, 12-, and 18- months, participants will repeat accelerometer wear protocols, 7-Day Physical Activity Recall interviews (by phone), and inperson assessment visits (weight, waist circumference, 2 Minute Step Test, psychosocial surveys) with local staff. Psychosocial surveys will also be distributed at 3-months to a assess potential mediators/ moderators of treatment efficacy. Participants will also complete surveys and exit interviews to assess program satisfaction and solicit feedback for improvement (at 12 months for the intervention arm and 18 months for the waitlist control arm). The wait-control group will be offered the 12 month DIAL intervention (same as intervention arm) after the 6 month assessment.

Throughout the project period, UAB research staff and Office of Community Outreach and Engagement county coordinators will report study progress via weekly emails and Zoom meetings. Surveys and in-depth qualitative interviews with participating Office of Community Outreach and Engagement county coordinators will be held to reflect on barriers and facilitators to implementing IVR-supported cancer prevention interventions in rural Black Belt counties, as well as issues surrounding sustainability and future large scale dissemination.

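### Section 5.2 releases assignments by closed envelope in 12 strata and states no custody, opening rule or block size; central release with undisclosed varying blocks would conceal them better

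*Combined protocol and SAP*

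**What the plan says.** All references are to the combined protocol and SAP.

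- **Release method.** Section 5.2 is the only description of allocation. The biostatistician "will prepare a closed envelope blocked randomization for the two treatment arms stratified by county and BMI group", with the sequence generated "using Proc Plan in SAS® Ver. 9.4". It does not say whether envelopes are sealed, opaque or numbered, who holds or opens them, where, or what the block size is.
- **Strata.** The counties are listed in Section 3.1 as "rural Black Belt (Marengo, Choctaw, Sumter, Hale, Greene, Dallas) counties in Alabama". The BMI groups in Section 5.2 are "BMI<30 and BMI>30, as this variable is known to be related to activity levels".
- **Timing.** Section 3.1: "After all assessment measures are complete, participants will be randomly assigned to a group". The sequence is consent, a measurement visit, seven days of accelerometer wear, a telephone recall interview, then allocation.
- **Local coordinators.** They host the information sessions at which screening takes place (Section 3.1). Section 4.4 adds that "assessments will be completed by local county coordinators (trusted individuals in the community"). They also help participants with barriers and lead walking groups as part of the intervention (Section 5.1.1).
- **Blinding.** The recall interviewers are described as blinded (Section 3.1), and so is the team that classifies adverse events (Section 8.3.4).
- **REDCap.** It is named once, for "psychosocial surveys in REDCap" (Section 3.1).

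**The concern.** Concealment means that nobody who can influence whether or when a person enters the trial knows the next assignment. A set of envelopes exists physically before each allocation and can be opened early, taken out of order or held back. With central release, the next assignment is not in the hands of field staff until the participant is registered.

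The setting makes this more than a formality. Participants know their arm. The coordinators who meet candidates, and who measure the height and weight that set the BMI stratum, also support the intervention. Each would come to know the assignment history of the two strata in a county. Allocation comes at least a week after the measurement visit, so the order of entry within a stratum depends partly on scheduling.

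At stake is the comparability of the arms on motivation. The primary outcome is self-reported activity, which motivation plausibly affects. If more motivated people were steered to DIAL, the 6-month difference would favour DIAL. Blinded interviewing, baseline before allocation and analysis by randomised arm would all leave that bias in place.

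**Working it through.** Section 5.2 gives no figure to reproduce. The check covers what is stated, what is missing, and which risk each remedy addresses.

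**1. Strata.** 6 counties × 2 BMI groups = 12. With the 240 participants of Section 8.2, 240/12 = 20 per stratum on average.

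**2. Two separate routes to foreknowledge.**
- *Handling of envelopes.* This depends on custody and opening, on which the documents are silent. It cannot be quantified. Central release removes it.
- *Prediction from past assignments.* This depends on block size and on who sees earlier assignments in the stratum. It is the same under envelopes and central release.

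**3. Size of the prediction route.** Block sizes are assumed, because none is given. In a permuted block of size 2m, with the size known and earlier assignments seen, the expected number of assignments known with certainty is 2m/(m+1). The share is therefore 1/(m+1). The best-guess rate comes from enumerating all balanced blocks.

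| Fixed block (assumed) | m | Share certain | Of 240, if all blocks are complete | Best guess correct |
|---|---|---|---|---|
| 2 | 1 | 1/2 = 50% | 120 | 75% |
| 4 | 2 | 1/3 = 33% | 80 | 71% |
| 6 | 3 | 1/4 = 25% | 60 | 68% |
| 8 | 4 | 1/5 = 20% | 48 | 67% |

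**4. Effect of varying blocks.** In a simulation with 20 participants per stratum and blocks of 4 and 6 mixed at random, guessing from the running imbalance was right in 68.5% of cases. The same rule gave 70.9% for fixed blocks of 4 and 67.0% for fixed blocks of 6. The gain is mainly in certainty: few or no assignments are certain if the sizes stay hidden. Informed guessing remains possible.

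**5. Effect on the design figures.** The noncentral t calculation for a difference of 35 and SD 90 at 80% power and two-sided 5% gives 104.8, which matches the 105 per arm in Section 8.2. Changing the release method leaves this as it is.

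**The case against.** The strongest reply is that exposure has not been shown. Section 5.2 says only that the biostatistician prepares the envelopes. Allocation follows accelerometer wear and a telephone interview by university staff, so it does not happen at the coordinator's visit, and custody at the university fits the text equally well. This stands: the documents do not establish local custody, still less tampering.

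Envelopes that are sealed, opaque, numbered and held by someone independent of recruitment can also conceal allocation. This is true in principle, but the plan states none of these safeguards.

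The motive to steer is limited. Participants must accept either arm (Section 4.1), and the wait list is offered the same programme after 6 months (Section 3.1). This lowers the risk without removing it.

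Baseline activity, self-efficacy, enjoyment and self-regulation are measured (Section 7.1), so an imbalance on them would be visible and could be adjusted for. This stands in part. The covariates that Section 8.3.2 names as examples are demographic, BMI and county variables, and unmeasured motivation would remain.

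A reader might go further in four ways that the documents do not support:
- *That the trial is unblinded.* The recall interviewers and adverse event classification are blinded; participants and coordinators are the ones who know the arm.
- *That the percentages in the table are a cost of envelopes, or that central release alone would end foreknowledge.* Those figures apply equally to central release with known fixed blocks.
- *That the bias can be sized.* Suppose steering raises the change in a share p of DIAL by d minutes and lowers it equally in the wait list, a bias of 2pd. Then p = 5% and d = 22.5 give 2.25 minutes (6% of the planned 35), while p = 10% and d = 45 give 9 minutes (26%). Neither p nor d has a source, so the answer is simply what is assumed.
- *That REDCap is ready to allocate.* It is named for surveys only.

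**Conclusion.** The concern holds as a weakness of the chosen method, not as evidence that allocation was or will be foreseen. The plan names a release method that is more open to tampering than central allocation, in 12 small strata, with no stated safeguard and with local staff who would learn assignments. A concretely better method is available at small cost, so this is more than a missing detail and should be changed.

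The size of any bias cannot be estimated from the documents. The prediction figures rest on assumed block sizes, on those sizes being known, and on earlier assignments in the stratum being visible. They support undisclosed varying blocks; they do not measure the harm of envelopes.

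**What to change.** In Section 5.2, replace the closed envelope with central release of the biostatistician's Proc Plan list. Use the REDCap randomisation function if the team has access to it, which is an assumption. Otherwise the biostatistician, or another person independent of recruitment, should release assignments. State that:

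- each assignment is released only after eligibility, county, BMI stratum and completion of baseline are recorded, with a log of the release;
- block sizes vary at random and are kept in a restricted document not available to recruiting or assessing staff.

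Recording the stratum first also requires a rule for a BMI of exactly 30, which the text as it reads places in neither group.

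If envelopes must be kept, the minimum is to specify sealed, opaque, sequentially numbered envelopes, custody independent of recruitment, and an opening log. If participants have already been allocated, the custody and opening practice actually used should be documented and reported.

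The cost is a short protocol change, brief set-up, and online or telephone contact at the moment of allocation. No sample size, power or alpha figure changes.

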5.3 STUDY INTERVENTION COMPLIANCE

A treatment fidelity plan based on the NIH's Behavioral Change Consortium framework will involve scripted treatment manuals, audio-recording of participant encounters, etc. Research staff will perform weekly IVR system audits to ensure that the IVR system is functioning properly; monitor the help line daily, which will be used by participants to report problems with DIAL system; and manually inspect feedback letters for accuracy before mailing to participants.

5.4 CONCOMITANT THERAPY

n/a

6 STUDY INTERVENTION DISCONTINUATION AND SUBJECT DISCONTINUATION/WITHDRAWAL

6.1 DISCONTINUATION OF STUDY INTERVENTION

n/a

6.2 SUBJECT DISCONTINUATION/WITHDRAWAL FROM THE STUDY

Subjects are free to withdraw from participation in the study at any time upon request. An investigator may discontinue or withdraw a subject from the study for the following reasons:

- Significant study intervention non-compliance
- If any clinical adverse event (AE), laboratory abnormality, or other medical condition or situation occurs such that continued participation in the study would not be in the best interest of the subject

Subjects who sign the informed consent form and are randomized but do not receive the study intervention may be replaced. Subjects who sign the informed consent form, and are randomized and receive the study intervention, and subsequently withdraw, or are withdrawn or discontinued from the study, will not be replaced.

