6.3 LOST TO FOLLOW-UP

A subject will be considered lost to follow-up if he or she fails to return for 2 scheduled visits and is unable to be contacted by the study site staff.

The following actions must be taken if a subject fails to be available for a required study visit:

- The site will attempt to contact the subject and reschedule the missed visit and counsel
 the subject on the importance of maintaining the assigned visit schedule and ascertain if
 the subject wishes to and/or should continue in the study.
- Before a subject is deemed lost to follow-up, the investigator or designee will make
 every effort to regain contact with the subject (where possible, 3 telephone calls and, if
 necessary, a letter to the subject's last known mailing address or local equivalent
 methods). These contact attempts should be documented in the subject's study file.
- Should the subject continue to be unreachable, he or she will be considered to have withdrawn from the study with a primary reason of lost to follow-up.

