8.2 SAMPLE SIZE DETERMINATION

Results from our previous UAB pilot study indicated an increase in minutes of moderate-to-vigorous physical activity among the DIAL intervention group compared with the control group. The SD of this measure was 90 minutes. Assuming a mean difference of 35 (SD 90) minutes in moderate-to-vigorous physical activity between the two groups from baseline to 6 months, a two-tailed two-group t test, and a significance level of 5%, we will have 80% power to detect this difference (with an effect size of 0.388) with 105 participants per arm (210 for the study). Assuming a mean change of 35 (SD 90) minutes in moderate-to-vigorous physical activity from baseline to 6 months for the intervention group, a two-tailed paired t test, and a significance level of 5%, we will have 80% power to detect this within-group change (with an effect size of 0.276) with 105 participants. Allowing for 15% attrition, we will recruit 240 participants (120 per arm).

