8.3 STATISTICAL ANALYSES

8.3.1 GENERAL APPROACH

Analyses will be performed on an intent-to-treat basis (ie, participants will be analyzed by the arms to which they were randomized). All statistical tests will be two-sided. All analyses will be performed using SAS, and *P*<.05 will be deemed statistically significant.

Although a large amount of missing data is not expected for any of our study variables, a sensitivity analysis may be performed using alternative methods for handling missing data (such as multiple imputation) to assess the most appropriate approach based on the amount of missing data and effect sizes observed.

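### Section 6.2 allows withdrawal from the study for intervention non-compliance; used before month 6, it would end follow-up in the DIAL arm only and could tilt the 6-month comparison slightly towards DIAL

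*Combined protocol and SAP*

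**What the plan says.** Section 6.2 introduces its list with "An investigator may discontinue or withdraw a subject from the study for the following reasons", and the first reason listed is "Significant study intervention non-compliance". The section sets no threshold and no time window. Section 6.1, on discontinuing the intervention, is marked n/a. The protocol therefore describes no route by which a non-complier stops the program but stays in follow-up.

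The arms differ in what there is to comply with. Under section 5.1.2, DIAL participants call the IVR system daily for three months and twice weekly in months 4-6. Under section 3.1, controls keep their usual routine until the 6-month assessment, and only then: "The wait-control group will be offered the 12 month DIAL intervention (same as intervention arm) after the 6 month assessment". Activity is first measured after baseline at 6 months, which is also the first primary time point.

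Other sections favour retention. Section 4.4: "In the case of 2 or more missed IVR intervention calls, staff will contact the participant". Section 6.3 asks for "every effort to regain contact with the subject" before anyone is declared lost.

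On analysis, section 8.3.1 says: "Analyses will be performed on an intent-to-treat basis (ie, participants will be analyzed by the arms to which they were randomized". It adds that a sensitivity analysis for missing data may be done. Section 8.3.2 names a repeated-measures mixed model. Section 8.3.5 compares completers and dropouts on baseline characteristics.

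**The concern.** Before month 6 the non-compliance reason can apply in one arm only, and it selects on behaviour after randomisation that is plausibly linked to the outcome. If the investigator withdraws DIAL participants who rarely call, and those people would have increased their activity less than the rest, the DIAL participants measured at month 6 are a favourable subset. The control arm undergoes no matching selection. The 6-month difference then exceeds the effect in everyone randomised, in the direction of the trial's hypothesis.

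This loss differs from ordinary dropout because the study team would create it, so it can be avoided.

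**Working it through.** **The plan's own figure.** Section 8.2 assumes a difference of 35 min/week, SD 90, two-sided 5% and 105 per arm. The noncentral t calculation gives power 0.801, so the stated 80% is reproduced. The section continues: "Allowing for 15% attrition, we will recruit 240 participants (120 per arm". Then 120 × 0.85 = 102 analysed per arm, with power 0.789. The 102 per arm is used below.

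**Would the planned analysis recover the lost outcomes?**
- Analysis by assigned arm says where a person is counted. It supplies no month-6 value for someone no longer followed.
- A person withdrawn before month 6 brings only a baseline value to the mixed model. IVR adherence is not among the covariates in section 8.3.2.
- The sensitivity analysis in section 8.3.1 is optional and its content is not specified.
- The comparison in section 8.3.5 describes baseline differences and adjusts nothing.

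**Size with no true effect.** The documents give neither the share p of DIAL withdrawn nor the correlation r between adherence and activity change. Both are assumed: p = 5% or 10% (6 or 12 of 120) and r = 0.1-0.2. The least adherent are withdrawn, other losses are random, and all losses fall within the 15% allowance.

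Bias = 90 × r × φ(z_p) / (1 − p), where φ(z_p) is 0.103 at 5% and 0.1755 at 10%. The standard error is 90 × √(2/102) = 12.6. The type I error is that of a two-sided z test shifted by bias/12.6.

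| p | r | Bias (min/week) | Bias / SE | Type I error |
|---|---|---|---|---|
| 5% | 0.1 | 0.98 | 0.08 | 5.1% |
| 5% | 0.2 | 1.95 | 0.16 | 5.3% |
| 10% | 0.1 | 1.75 | 0.14 | 5.2% |
| 10% | 0.2 | 3.51 | 0.28 | 5.9% |

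**Why r stops at 0.2.** The withdrawn group lies 90 × r × φ(z_p) / p below the arm mean. At r = 0.2 that is 37 min/week (5%) or 32 (10%). At r = 0.3 it is 56 or 47, which is hard to reconcile with entry being limited to people "insufficiently active (engaging in moderate-vigorous physical activity< 60 minutes per week": they have little activity to lose.

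**Simulation respecting those limits.** Assumptions: baseline uniform on 0-60, follow-up gamma with mean 60 and SD 91 (so never negative), SD of change 90, the same mean change in both arms, 40,000 trials per cell.

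| p | r | Bias (min/week) | Type I error |
|---|---|---|---|
| 5% | 0.10 | 0.80 | 4.9% |
| 5% | 0.20 | 1.48 | 5.0% |
| 10% | 0.10 | 1.64 | 5.1% |
| 10% | 0.20 | 3.04 | 5.8% |

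The Monte Carlo standard error is 0.06 for bias and 0.1 percentage point for type I error. A likelihood model using baseline and month 6 gave 0.81, 1.48, 1.64 and 3.04 in the same order, so it did not remove the bias. The exact values depend on how adherence is tied to a skewed outcome. A smaller repeat run with a linear link gave biases inside the same range.

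**Size with a true effect.** If adherers gain 35 min/week and non-adherers nothing, the full-arm effect is 35 × (1 − p), which is 33.25 or 31.5. Dropping the non-adherers returns 35, an overstatement of 1.75 or 3.5 min/week (5% or 11%).

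**The case against.** The strongest reply is that the rule will seldom be used and matters little. It is permissive. The same list mentions laboratory abnormalities, although section 7.1 contains no laboratory test, which suggests template text rather than planned practice. The working response to missed calls is the staff contact in section 4.4. Sections 2.3.1 and 8.3.4 describe pausing the activity program for health symptoms without saying that the person leaves the study. All of this stands, and it makes routine use less likely. None of it says that a person withdrawn under section 6.2 is still assessed.

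A second reply is that low adherers are also the people most likely to leave or miss visits anyway. This stands too. The calculation compares use of the rule with full observation of these people, so it gives an upper bound on the rule's own contribution.

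A third is that IVR-reported activity and the 3-month survey could support multiple imputation, which section 8.3.1 names. They could, but the plan does not commit to it.

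A reader might also infer more than the documents support:
- *That section 6.2 contradicts the intent-to-treat statement.* It does not, because that statement only assigns people to arms.
- *That the 6-month result will be inflated.* Nothing shows how often the rule would be used or that low adherers gain less.
- *That the whole 15% attrition allowance could be such withdrawals.* This leaves no room for any other loss in DIAL and is not a reasonable basis for a headline figure.
- *That the one-sidedness persists.* The argument is confined to withdrawals before month 6; afterwards both arms can be on DIAL.

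**Conclusion.** The point holds in conditional form. Section 6.2 permits a loss of follow-up that, before month 6, can arise only in the DIAL arm, and the analysis plan contains no firm step that would correct it. The direction rests on the assumption that low adherers gain less activity.

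With 5-10% of DIAL withdrawn and correlations of 0.1-0.2, all assumed, the bias is about 1.0-3.5 min/week in closed form and 0.8-3.0 in the simulation, against a design difference of 35. Type I error is about 5.1-5.9% and 4.9-5.8% respectively. At 5% withdrawn, the simulation shows no detectable inflation. With few or no withdrawals the bias is negligible. This is a minor weakness, worth closing because the remedy is cheap.

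**What to change.** In section 6.2, remove intervention non-compliance as a reason for withdrawal from the study. State that participants who stop or do not follow the IVR program are still asked to complete the scheduled 6-, 12- and 18-month PAR and accelerometer assessments, unless they withdraw consent or are withdrawn under the existing medical reason, which is unchanged. This reduces the bias. It does not deal with low adherers who leave of their own accord or miss visits.

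The cost is protocol wording plus contacts that are already scheduled. Keeping non-adherers may dilute the estimated effect, as analysis of everyone randomised implies. If 5% of DIAL gain nothing, the difference is 35 × 0.95 = 33.25, and power with 108 DIAL and 102 control participants is about 76%. If 10% gain nothing, it is 35 × 0.90 = 31.5, and power with 114 and 102 is about 72%. The reference is 79% at the full 35 minutes with 102 per arm. This cost arises only if the 35-minute target does not already allow for non-adherers, and section 8.2 does not say whether it does.
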